3.7.2 Initiation of Therapy

Participants must be registered with the DF/HCC CTMS before the initiation of treatment or other protocol-specific interventions. Treatment and other protocol-specific interventions may not be initiated until the Participating Institution receives confirmation of the participant's registration from the Coordinating Center. The DF/HCC Sponsor and DFCI IRB must be notified of any violations to this policy.

3.7.3 Eligibility Exceptions

No exceptions to the eligibility requirements for a protocol without DFCI IRB approval will be permitted. All Participating Institutions are required to fully comply with this requirement. The lead site will provide the appropriate paperwork to submit an eligibility exception request at the time of study start up.

3.8 DF/HCC Protocol Case Number

At the time of registration, the following identifiers are required for all subjects: initials, date of birth, gender, race and ethnicity. Once eligibility has been established and the participant successfully registered, the participant is assigned a unique protocol case number. Participating Institutions should submit all de-identified subsequent communication and documents to the Coordinating Center, using this case number to identify the subject.

CONFIDENTIAL

This document is confidential. Do not disclose or use except as authorized.

3.8.1 Protocol Deviations, Exceptions and Violations

Federal Regulations require an IRB to review proposed changes in a research activity to ensure that researchers do not initiate changes in approved research without IRB review and approval, except when necessary to eliminate apparent immediate hazards to the participant. DF/HCC requires all departures from the defined procedures set forth in the IRB approved protocol to be reported to the DF/HCC Sponsor, who in turn is responsible for reporting to the DFCI IRB.

For reporting purposes, DF/HCC uses the terms “violation”, “deviation” and “exception” to describe departures from a protocol. All Participating Institutions must adhere to these requirements for reporting to the DF/HCC Sponsor and will follow their institutional policy for reporting to their local IRB.

3.8.2 Definitions

Protocol Deviation: Any departure from the defined procedures set forth in the IRB-approved protocol which is *prospectively approved* prior to its implementation.

Protocol Exception: Any protocol deviation that relates to the eligibility criteria, e.g. enrollment of a participant who does not meet all inclusion/exclusion criteria.

Protocol Violation: Any protocol departure that was not *prospectively approved* by the IRB prior to its initiation or implementation.

3.8.3 Reporting Procedures

DF/HCC Sponsor: is responsible for ensuring that clear documentation is available in the medical record and/or regulatory documents to describe all protocol exceptions, deviations and violations. The DF/HCC Sponsor will also be responsible for ensuring that all protocol violations/deviations are promptly reported per DFCI IRB guidelines.

Participating Institutions: Protocol deviations require prospective approval from the DFCI IRB. The Participating Institution must submit the deviation request to the Coordinating Center who will then submit the deviation request to the DFCI IRB. Upon DFCI IRB approval the deviation is submitted to the Participating Institution IRB, per institutional policy. A copy of the Participating Institution’s IRB report and determination will be forwarded to the Coordinating Center within 10 business days after the original submission. The deviation may not be implemented without all required approvals.

All protocol violations must be sent to the Coordinating Center in a timely manner. The Coordinating Center will provide training for the requirements for the reporting of violations.

Coordinating Center: Upon receipt of the violation/deviation report from the Participating Institution, the Coordinating Center will submit the report to the DF/HCC Sponsor for review. Subsequently, the Participating Institution’s IRB violation/deviation report will be submitted to the DFCI IRB for review per DFCI IRB reporting guidelines. DF/HCC will forward all violation reports to CTEP via an internal DF/HCC process, as applicable.

CONFIDENTIAL

This document is confidential. Do not disclose or use except as authorized.

3.9 Safety Assessments and Toxicity Monitoring

The study teams at all participating institutions are responsible for protecting the safety, rights and well-being of study participants. Recording and reporting of adverse events that occur during the course of a study help ensure the continuing safety of study participants.

All participants receiving investigational agents and/or other protocol mandated therapy will be evaluated for safety. The safety parameters include all laboratory tests and hematological abnormalities, physical examination findings, and spontaneous reports of adverse events reported by participants. All toxicities encountered during the study will be evaluated according to the NCI criteria specified in the protocol. Life-threatening toxicities must be reported immediately to the DF/HCC Sponsor via the Coordinating Center.

Additional safety assessments and toxicity monitoring will be outlined in the protocol.

3.9.1 Guidelines for Reporting Serious Adverse Events

Guidelines for reporting Adverse Events (AEs) and Serious Adverse Events (SAEs) are detailed in protocol section 7 of the protocol.

Participating Institutions must report the SAEs to the DF/HCC Sponsor and the Coordinating Center following the [DFCI IRB Adverse Event Reporting Policy](#).

The Coordinating Center will maintain documentation of all Participating Institution Adverse Event reports and be responsible for communicating to all participating investigators, any observations reportable under the DFCI IRB Reporting Requirements. Participating Institutions will review and submit to their IRB according to their institutional policies and procedures

3.9.2 Guidelines for Processing IND Safety Reports

The DF/HCC Sponsor will review all IND Safety Reports and ensure that all IND Safety Reports are distributed to the Participating Institutions. Participating Institutions will review/submit to their IRB according to their institutional policies and procedures.

3.10 Data Management

DF/HCC CTRIO develops case report forms (CRF/eCRFs), for use with the protocol. These forms are designed to collect data for each study. DF/HCC CTRIO provides a web based training for all eCRF users.

3.10.1 Data Forms Review

Data submissions are monitored for timeliness and completeness of submission. If study forms are received with missing or questionable data, the submitting institution will receive a written or electronic query from the DF/HCC Office of Data Quality, Coordinating Center, or designee.

CONFIDENTIAL

This document is confidential. Do not disclose or use except as authorized.

Responses may be returned on the written query or on an amended paper case report form, or in the case of electronic queries, within the electronic data capture (eDC) system. In the case of a written query for data submitted on a paper case report form, the query must be attached to the specific data being re-submitted in response.

If study forms are not submitted on schedule, the Participating Institution will periodically receive a Missing Form Report from the Coordinating Center noting the missing forms.

4. REQUISITIONING INVESTIGATIONAL DRUG

The ordering of investigational agent is specified in the protocol section 8 of the protocol.

Participating Institutions should order their own agent regardless of the supplier.

If the agent is commercially available, check with the local Director of Pharmacy and/or the Research Pharmacy to ensure that the agent is in stock. If the agent is not stocked, ensure that the agent can be ordered once the protocol is approved by the local IRB.

If the agent is investigational, ensure that the pharmacy will be able to receive and store the agent according to state and federal requirements. The local IRB should be kept informed of who will supply the agent so that any regulatory responsibilities can be met in a timely fashion

5. MONITORING: QUALITY CONTROL

The quality control process for a clinical trial requires verification of protocol compliance and data accuracy. The Coordinating Center, with the aid of the DF/HCC Office of Data Quality, provides quality control oversight for the protocol.

5.1 Ongoing Monitoring of Protocol Compliance

The Participating Institutions may be required to submit participant source documents to the Coordinating Center for monitoring. Participating Institution may also be subject to on-site monitoring conducted by the Coordinating Center.

The DF/HCC lead site will implement ongoing monitoring activities to ensure that Participating Institutions are complying with regulatory and protocol requirements, data quality, and participant safety. Monitoring practices may include but are not limited to source data verification, and review and analysis of eligibility requirements, informed consent procedures, adverse events and all associated documentation, review of study drug administration/treatment, regulatory files, protocol departures reporting, pharmacy records, response assessments, and data management.

Monitoring practices may include but are not limited to; source verification, review and analysis of the following: eligibility requirements of all participants, informed consent procedures, adverse events and all associated documentation, study drug administration / treatment, regulatory records and site trial master files, protocol deviations, pharmacy records, response assessments, and data management. Additionally, regular and

CONFIDENTIAL

This document is confidential. Do not disclose or use except as authorized.

ongoing communication with Participating Institutions will be accomplished by holding all site teleconferences at least monthly. The Lead Institution will keep in close touch with the Participating Institutions via email and phone. Source documents from Participating Institutions, will be collected at specific data points that support the primary and or secondary endpoints

Remote/ Virtual Monitoring

The Coordinating Center will request source documentation from Participating Institutions as needed to complete monitoring activities. Participating Institutions will be asked to forward de-identified copies of participants' medical record and source documents to the Coordinating Center to aid in source documentation verification.

On-Site Monitoring

On-Site Monitoring: On-site monitoring will occur at least once per year depending on a site's accrual. Participating Institutions will be required to provide access to participants' complete medical record and source documents for source documentation verification during the on-site visit. In addition, upon request from a monitor or auditor, Participating Institutions should provide access to regulatory documents, pharmacy records, local policies related to the conduct of research, and any other trial-related documentation maintained by the participating site. If there are concerns for protocol compliance, issues that impact subject safety or the integrity of the study are found, or trends identified based on areas of need, additional monitoring visits may be scheduled. On site monitoring visits can be supplemented with virtual monitoring assessments, provided that the minimum monitoring frequencies are adhered to.

5.2 Monitoring Reports

The DF/HCC Sponsor will review all monitoring reports to ensure protocol compliance. The DF/HCC Sponsor may increase the monitoring activities at Participating Institutions that are unable to comply with the protocol, DF/HCC Sponsor requirements or federal and local regulations.

5.3 Accrual Monitoring

Prior to extending a protocol to an external site, the DF/HCC Sponsor will establish accrual requirements for each participating institution. Accrual will be monitored for each participating institution by the DF/HCC Sponsor or designee. Sites that are not meeting their accrual expectations may be subject to a formal letter regarding accrual expectations, or termination. Due to the small patient population of this trial, the accrual minimum requirement is at least one patient every year.

6. AUDITING: QUALITY ASSURANCE

Auditing is a method of Quality Assurance and involves the systematic and independent examination of all trial related activities and documents. Audits determine if evaluated activities were appropriately conducted and whether data was generated, recorded and analyzed, and accurately reported per the protocol, applicable Standard Operating Procedures (SOPs), and the Code of Federal Regulations (CFR).

CONFIDENTIAL

This document is confidential. Do not disclose or use except as authorized.

6.1 DF/HCC Internal Audits

All Participating Institutions are subject to audit by the DF/HCC Office of Data Quality (ODQ). Typically, approximately 3-4 participants would be audited at the site over a 2 day period. If violations which impact participant safety or the integrity of the study are found, more participant records may be audited.

6.2 Audit Notifications

It is the Participating Institution's responsibility to notify the Coordinating Center of all scheduled audit dates (internal or NCI) and re-audit dates (if applicable), which involve this protocol. All institutions will forward a copy of final audit and/or re-audit reports and corrective action plans (if applicable) to the Coordinating Center, within 12 weeks after the audit date.

6.3 Audit Reports

The DF/HCC Sponsor will review all final audit reports and corrective action plans, if applicable. The Coordinating Center, must forward any reports to the DF/HCC ODQ per DF/HCC policy for review by the DF/HCC Audit Committee. For unacceptable audits, the DF/HCC Audit Committee would forward the final audit report and corrective action plan to the DFCI IRB as applicable.

***** Remember to check the ALERT PAGE*****

SPECIAL NURSING CONSIDERATIONS UNIQUE TO THIS PROTOCOL

Study Design	
Nivolumab is a fully human monoclonal antibody that targets the PD-1 cell surface membrane receptor. Nivolumab inhibits the interaction of PD-1 with its ligands, PD-L1 and PD-L2, resulting in enhanced T-cell proliferation and interferon-gamma (IFN-γ) release in vitro. Lenalidomide (REVLIMID) is a thalidomide analogue, is an immunomodulatory agent with antiangiogenic properties. Dexamethasone is a synthetic adrenocortical steroid.
 
 • The Study Design is in Section 1.1 • The Study Rationale is in Section 2.9 • A cycle is defined as 28 days in Section 5.1
Dose Calc.	
 • Nivolumab is dosed in fixed dosing, 240 mg IV • Lenalidomide is dosed in fixed dosing, between 5-25 mg (increments of 5 mg for dose reductions) • Dexamethasone is dosed in fixed dosing, 40 mg or 20 mg or 10 mg for dose reductions
Study Drug Administration	
Agent Administration Guidelines are found in Section 5.2
 
 • Nivolumab is given IV every other week on Days 1&15; Lenalidomide is PO Days 1-21; Dexamethasone is PO Days 1, 8, 15 for Cycles 1-6 ONLY • Nivolumab is given IV over 60 minutes (+/- 10 minutes); No standard premeds required, unless history of infusion reaction. A 60 min post-infusion observation period is suggested, especially during first 2 cycles, but not mandatory per protocol. • The drugs may be administered in any order. • Criteria to treat DAY 1: ANC\geq1,000; PLT\geq50; Other drug related, non-heme tox \leqGrade 1 or baseline. • Criteria to treat DAY 15: For Lenalidomide: ANC\geq1,000; PLT\geq30; Hgb\geq8 Other drug related less than Grade 3 or baseline. For Nivolumab: AST\leq90; ALT\leq156; Bilirubin\leq1.8; Creatinine\leq1.95 or \leq1.5 x baseline • Fasting is not required. • Lenalidomide capsules and Dexamethasone tablets should be swallowed whole, and should not be broken, chewed or opened. Administration should be at approximately the same time each day. If a dose is missed and less than 12 hours has elapsed since the missed dose, the patient may take the dose for that day. If more than 12 hours has elapsed since missing a dose at the normal time, the patient should not take the dose, but take the next dose at the normal time on the following day. If a dose is missed, it should be taken as soon as possible on the same day. If a dose is vomited, the dose should not be made up and the participant should continue with the regular schedule of the drug at the next dose.
Dose Mods & Toxicity	
Dose Modifications/Dosing Delay for Toxicity are outlined in Section
 
 • This protocol uses NCI CTCAE criteria, version 4.03 • There are no dose modifications for Nivolumab, there are dose reductions per protocol for Lenalidomide and Dexamethasone.
Con Meds	
Concomitant Therapy Guidelines are in Section 5.3.1
 
 • Stem cell mobilization and collection may be performed at time of best response or after 6 cycles of therapy. • Filgrastim is allowed, pegfilgrastim is NOT. • Transfusions and supportive care are allowed; bisphosphonate therapy included.

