6.3 Lenalidomide

Hematologic Toxicities: For adverse hematologic events that are considered possibly, probably or definitely related to Lenalidomide, the following criteria for retreatment and dose modification should be followed unless discussed and approved first by the overall principal

CONFIDENTIAL

This document is confidential. Do not disclose or use except as authorized.

investigator. The treating investigator should determine the clinical significance of laboratory values and attribution to study medications before a treatment decision is made. All instances where lenalidomide is held, the dose will be considered missed, and will not be made up.

Non Hematologic Toxicity: For adverse non hematologic events that are considered to be possibly, probably or definitely related to Lenalidomide, the following criteria for retreatment and dose modification should be followed unless discussed and approved first by the overall principal investigator. The treating investigator should determine the clinical significance of laboratory values or radiographic findings and attribution to study medications before a treatment decision is made. All instances where lenalidomide is held, the dose will be considered missed, and will not be made up.

Dose delays and modifications should be made as indicated in the following table(s) unless first discussed with the Overall PI. The descriptions and grading scales found in the revised NCI Common Terminology Criteria for Adverse Events (CTCAE) version 4.0 will be utilized for dose delays and dose modifications. A copy of the CTCAE version 4.0 can be downloaded from the CTEP website

http://ctep.cancer.gov/protocolDevelopment/electronic_applications/ctc.htm.

Table 12 Lenalidomide Hematologic Toxicities

CTCAE 4.0 Category	CTCAE Grade	Lenalidomide Dose Modification
Absolute Neutrophil Count (ANC)¹	Grade 1 or Grade 2	Continue to treat- Do NOT OMIT and DO NOT REDUCE therapy
	Grade 3	Hold dose Administer Filgrastim Resume at same dose when ANC is \geq 1000 if neutropenia is the only hematologic toxicity If other hematologic toxicity \geq Grade 2 is present, reduce dose one level when ANC \geq 1000
	Grade 4	Hold dose Administer Filgrastim Resume therapy at one dose level lower when ANC is \geq 1000
Neutropenia with Fever ANC <1000 and temperature \geq 38.5° C or 101°F	Grade 3 or Grade 4	Hold dose Administer Filgrastim Reduce dose one level when ANC \geq 1000

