Thrombocytopenia	Grade 1 or Grade 2	Continue to treat- Do NOT OMIT and DO NOT REDUCE therapy

CONFIDENTIAL

This document is confidential. Do not disclose or use except as authorized.

Aspirin prophylaxis should be held if platelets are $\leq 50,000$	Grade 3 or Grade 4	
Provide platelet transfusion support Redraw platelets
 
If redrawn platelet value $\geq 50,000$ -> Do NOT OMIT and DO NOT REDUCE therapy
 
If redrawn platelet value $< 50,000$ continue to transfuse at the discretion of the investigator and hold therapy until platelets are $\geq 50,000$ on Day 1 or $\geq 30,000$ intracycle
 
Resume therapy at one dose level lower when the patient's platelets are $\geq 50,000$ on Day 1 or $\geq 30,000$ intracycle

	Grade 1 Grade 2 Grade 3	
Continue to treat- Do NOT OMIT and DO NOT REDUCE therapy Transfuse at the discretion of treating investigator

Anemia	Grade 4	
Hold treatment Transfuse Resume treatment when hemoglobin ≥ 8.0 g/dL DO NOT REDUCE therapy

¹ ANC can be calculated two ways: From the percentage of neutrophils: White Blood Count (WBC) x total neutrophils (polys% + bands%) x 10. From the absolute number of cells: (Absolute polys + Absolute bands) x 10.

Table 13 Lenalidomide Non Hematologic Toxicities

CTCAE 4.0 Category	CTCAE Grade	Lenalidomide Dose Modification
Infection or Viral Illness with ANC¹ ≥ 1000 Including herpes zoster reactivation	N/A	
Day 1 of Cycle: Delay cycle until infection/viral illness has resolved. Resume treatment at the same dose level. Do not dose reduce.
 
Intracycle: Hold lenalidomide for a maximum of 21 days to allow for recovery. Resume treatment at same dose level.
 
If patient has delay of greater than 21 days, the patient must come off-study

CONFIDENTIAL

This document is confidential. Do not disclose or use except as authorized.

Infection or Viral Illness with ANC¹ < 1000	N/A	
Day 1 of Cycle: Delay cycle until infection/viral illness has resolved. Administer filgrastim or equivalent as indicated.
 
Reduce one dose level when infection/virus has resolved, and ANC \geq1000
 
Intracycle: Hold lenalidomide for a maximum of 21 days. Reduce one dose level when infection/virus has resolved and ANC \geq 500
 
If patient has a delay of less than or equal to 21 days, dose reduce to next dose level. If patient has delay of greater than 21 days, the patient must come off-study

--	------------	---

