Allergic reaction or hypersensitivity to Lenalidomide Including Rash related to Lenalidomide	Grade 1 Grade 2 Grade 3 or Grade 4	
Continue to treat- Do NOT OMIT and DO NOT REDUCE therapy
 
Continue to treat- Do NOT OMIT and DO NOT REDUCE therapy
 
Hold lenalidomide Follow at least weekly. If toxicity resolves to \leq grade 2, restart at next lower dose level

Renal/Metabolic For all grades, provide hydration and other supportive care as needed at the discretion of the treating investigator	Grade 1 Grade 2 Grade 3 or Grade 4	
Continue to treat- Do NOT OMIT and DO NOT REDUCE therapy
 
Hold Lenalidomide until < grade 2 and resume treatment at the same dose level If toxicity recurs, dose reduce one dose level at the treating investigator's discretion
 
Hold Lenalidomide until < grade 2 and resume treatment with one dose level reduction If the toxicity remains \geq grade 3, omit dose and restart at subsequent scheduled visit with one dose level

CONFIDENTIAL

This document is confidential. Do not disclose or use except as authorized.

		reduction If treatment-related toxicity occurs on day one of the cycle, the cycle will be delayed.
--	--	---

Diarrhea, Constipation, Nausea, or Vomiting	Grade 1	Continue to treat- Do NOT OMIT and DO NOT REDUCE therapy
	Grade 2	Treat at the discretion of the investigator Provide aggressive supportive care DO NOT REDUCE therapy
	Grade 3	Hold Lenalidomide until toxicity resolves to < grade 2 If the patient has received maximum supportive care, resume therapy with one dose level reduction
	Grade 4	Hold Lenalidomide until toxicity resolves to < grade 2 Resume therapy with one dose level reduction
All other related toxicities not listed previously in this table	Grade 1	Continue to treat- Do NOT OMIT and DO NOT REDUCE therapy
	Grade 2	Continue to treat- Do NOT OMIT and DO NOT REDUCE therapy unless considered to be a clinically significant finding Provide supportive care as needed

CONFIDENTIAL

This document is confidential. Do not disclose or use except as authorized.

	Grade 3	Hold Lenalidomide until toxicity resolves to < grade 2 Resume therapy with one dose level reduction at the discretion of the treating investigator

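### The nursing page's Day 15 lenalidomide limit is looser than Table 13 for Grade 1-2 related infection with ANC of at least 1000 and for Grade 2 renal/metabolic toxicity

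*Combined protocol and SAP*

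**What the plan says.** The Study Drug Administration row of the nursing page (Special Nursing Considerations) lists criteria to treat on Day 1 and on Day 15. On Day 15, lenalidomide may be given if ANC is at least 1,000, platelets are at least 30, haemoglobin is at least 8, and for the rest: "Other drug related less than Grade 3 or baseline". A separate Day 15 line for nivolumab gives limits for AST, ALT, bilirubin and creatinine.

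Section 6.3 of the protocol sets the governing rules. Table 13 applies "For adverse non hematologic events that are considered to be possibly, probably or definitely related to Lenalidomide", and the section adds: "Dose delays and modifications should be made as indicated in the following table(s) unless first discussed with the Overall PI". Three of its instructions matter here:

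- Infection or viral illness with ANC of at least 1000. The grade column is marked not applicable, and the mid-cycle instruction is "Hold lenalidomide for a maximum of 21 days to allow for recovery".
- Renal/metabolic, Grade 2: "Hold Lenalidomide until < grade 2 and resume treatment at the same dose level".
- Renal/metabolic, Grade 3 or 4: "Hold Lenalidomide until < grade 2 and resume treatment with one dose level reduction". The Grade 3 gastrointestinal entry has the same release level: "Hold Lenalidomide until toxicity resolves to < grade 2 If the patient has received maximum supportive care".

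**The concern.** The page is worded as a working checklist, and one threshold stands in for six Table 13 rows that have different triggers and release levels. A nurse checking a mid-cycle patient against it could clear lenalidomide where the protocol says to hold.

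The triggers are foreseeable. Section 7.2.1.3 lists upper respiratory infection in more than 10% of lenalidomide-treated individuals, and renal failure, pneumonia and sepsis in more than 1%. The line is also still in use: Section 5.1 stops nivolumab and accrual, but participants may stay on lenalidomide with or without dexamethasone. At stake are dosing safety and avoidable protocol violations, not the trial's inference.

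**Working it through.** No arithmetic beyond counting applies. The check sets the page's Day 15 line beside each part of Section 6.3.

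**Step 1: blood counts.** Table 12 resumes lenalidomide at ANC of at least 1000, platelets of at least 30,000 mid-cycle, and haemoglobin of at least 8.0 g/dL. The page uses the same three levels. Its Day 1 criteria also match Section 6.1. The page is evidently meant to summarise the protocol, and the Day 15 non-haematologic phrase is where it departs.

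**Step 2: when to hold mid-cycle (lenalidomide-related events only).**

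| Table 13 row | Table 13 holds at | Page holds at | Result |
|---|---|---|---|
| Infection, ANC at least 1000 | any grade | Grade 3 or higher | differs at Grade 1-2 |
| Infection, ANC below 1000 | any grade | any grade, through the ANC limit | agrees at onset |
| Allergic reaction/rash | Grade 3-4 | Grade 3-4 | agrees |
| Renal/metabolic | Grade 2 or higher | Grade 3 or higher | differs at Grade 2 |
| Diarrhoea, constipation, nausea, vomiting | Grade 3-4 | Grade 3-4 | agrees |
| All other related | Grade 3-4 (Grade 2 continues unless clinically significant) | Grade 3-4 | agrees by default |

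Two of six rows differ, and in both the page is the looser rule. A related infection is itself a drug-related toxicity, so the page's general limit stops it at Grade 3 or higher; only Grade 1-2 gets through. The page's creatinine limit does not close the renal gap, because it belongs to the nivolumab line.

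**Step 3: restarting after a Grade 3-4 hold, if the line is used for that.** Read this way, the page releases at Grade 2 or less.

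- Rash: Table 13 also releases at Grade 2 or less, so they agree.
- Renal/metabolic, gastrointestinal and all other: Table 13's stated level is below Grade 2, so they differ.

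That is 3 of the 4 graded rows. The renal/metabolic row is less clean than the other two. It also says that if toxicity stays at Grade 3 or higher, the dose is omitted and treatment restarts one level lower at the next scheduled visit.

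**Step 4: the opposite direction.** For infection with ANC below 1000, the Day 1 instruction is "Reduce one dose level when infection/virus has resolved, and ANC" is at least 1000. The mid-cycle instruction in the same row lowers the ANC level to 500, again once the infection has resolved. At ANC 500 to 999 with the infection resolved, this row allows a restart at reduced dose, while the page, which requires 1,000, still holds. The page's figure is Table 12's resume level, so here the page is stricter than one Table 13 row.

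**The case against.** The strongest reply is that the page is subordinate and has little reach. Section 6.3 has the treating investigator judge significance and attribution before any treatment decision. Lenalidomide is taken by mouth and may be shipped to the patient's home (Section 8.2.8). The study calendar has no Day 15 column, and with nivolumab stopped little brings a patient in on that day. The page's row on dose modifications already refers to the protocol, although its section number is blank in the text available. Other nursing pages, including an alert page that staff are told to check, were removed before review and could carry an infection or renal instruction.

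All of this lowers the chance of harm and limits the finding to the lines shown. It does not reconcile the two rules: someone who follows the Day 15 line as written, without consulting the Overall PI, departs from Table 13.

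Four stronger readings are tempting, and the documents do not support them:

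- A reader might infer that the page clears lenalidomide during serious related infection. It does not, because Grade 3 or higher fails the general limit.
- A reader might infer that every difference runs toward dosing. The low-ANC infection row runs the other way.
- A reader might take the line as setting a restart level of Grade 2. It never mentions resuming after a hold, so that mismatch depends on how staff use it.
- A reader might size the exposure by counting the Day 15 dates left after the version date. Those are calendar dates, not visits, and the documents do not say how many patients remain on lenalidomide.

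**Conclusion.** The inconsistency is real and minor. For two hold triggers the page permits lenalidomide where Table 13 holds it: Grade 1-2 related infection or viral illness with ANC of at least 1000, and Grade 2 related renal/metabolic toxicity. The restart difference is conditional on the line being used for patients already on hold.

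The conclusion assumes that the events are judged at least possibly related to lenalidomide, that the Overall PI has not approved a departure, and that no removed nursing page supplies the missing limits. How often the difference would change a dosing decision cannot be estimated from the documents. Endpoints, power and error rates are unaffected.

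**What to change.** Replace the Day 15 lenalidomide limits on the nursing page with a pointer to Section 6.3, Tables 12 and 13, so that only one set of limits exists. Supply the section number in the page's dose-modification row if it is blank in the document as issued.

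If limits are to stay on the page, add: no active related infection or viral illness of any grade; renal/metabolic toxicity below Grade 2; after a Grade 3-4 hold, restart according to Table 13.

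The cost is rewording one line and filling in one cross-reference. No visit, assessment or protocol criterion is added.
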